### 9.7.3 Analysis of primary objectives

With regard to objective #1, the descriptive statistics including the number of events (n) and prevalence (%) will be presented for each pregnancy outcome (i.e. serious adverse pregnancy outcome, elective TOPFA, MCA, stillbirth, and live birth) in each study cohort separately and also for the whole study population. Information on live births, stillbirths and TOPFAs will be included in the analyses of MCA, as approximately 10% of MCAs are detected in foetuses of TOPFA.

With regard to objective #2, the prevalence of the serious adverse pregnancy outcomes will be compared between the study cohorts using log-binomial regression. Two models, base and adjusted, will be used in these comparisons. The base model will be adjusted for the following design variables and *a priori* likely confounders: country, year of pregnancy outcome, maternal age at LMP, number of previous pregnancies, any chronic diseases, and exposure to any teratogenic medications including steroids.

The adjusted model will be built using a variable selection procedure (Bursac et al. 2008). Candidate covariates for the adjusted model will be those in the base model and the following additional ones: university hospital district, pre-pregnancy weight, pre-pregnancy BMI, number of previous abortions, smoking status during pregnancy, number of foetuses in pregnancy (single vs. multiple), time since MS diagnosis and duration of MS treatment as available in the data sources. Variable selection starts by applying first the unadjusted model and proceeds as follows:

1. Each candidate covariate will be considered a potential confounder if the univariate association between the covariate and the serious adverse pregnancy outcome, tested with the Wald test for logistic regression with *P*-value cut-point of 0.25.
2. All candidate covariates identified as potential confounders in step 1 will be added simultaneously to the model. After this, additional covariates not identified as potential confounders in step 1 will be added to the model one at a time and the model fit comparing each null vs alternative model will be assessed by the likelihood-ratio test. Variables in the alternate model will be retained at a likelihood ratio test of *P*-value <0.1.
3. An iterative process of reducing the model in step 2 will be performed by refitting and verifying model fit comparing null vs. alternative models by likelihood ratio test of *P*-value <0.1 to determine the main effects model.
4. Model fit results and the effect of adding and removing variables in step 2 and step 3 will be reported at each step. If there are a low number of outcomes identified, the final adjusted model will be limited to a covariate-outcome ratio of 1 covariate: 10 outcomes to avoid over-adjustment. If the number of covariates is higher than the covariate-outcome ratio allows, then the covariates with least significant effect to the model fit will be omitted.

Comparisons will be made separately for different study cohorts: i) one comparison will be made between women with MS exposed to IFN- $\beta$  only (cohort 1) vs. unexposed to any MSDMDs (cohort 3) and ii) another between women with MS exposed to IFN- $\beta$  only (cohort 1) vs. unexposed to IFN- $\beta$  regardless of exposure to other MSDMDs (cohort 4). The RR estimates with 95% CIs and associated *p*-values will be reported for these comparisons and for all relevant covariates used in the model.

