#### **Potential confounding factors and effect modifiers:**

The following confounding factors and effect modifiers will be taken into account in the analyses according to availability and available time period from each register source: any chronic diseases, exposure to any teratogenic medications including steroids, country of residence of the mother, university hospital district, maternal age at LMP, year of pregnancy outcome, pre-pregnancy weight, pre-pregnancy BMI, number of previous pregnancies, time since MS diagnosis, duration of MS treatment, number of previous abortions, smoking status during pregnancy and number of foetuses in the pregnancy (single or multiple).

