The estimated background prevalence for the composite endpoint of serious adverse pregnancy outcome, consisting of TOPFAs, live births with MCA and all stillbirths, was 6.5% (personal communication with [name], THL, 15 May 2014) and 7.3% (= 24/331, based on the feasibility study in Finland, cf. Annex 1) in women with MS unexposed to IFN- $\beta$  (regardless of exposure to other MSDMDs) and unexposed to any MSDMD, respectively. Because these numbers best correspond to the study setting, they were taken as the most relevant baseline prevalences of serious adverse pregnancy outcomes in the sample size calculations. Lower outcome prevalences were investigated to test how sensitive the findings of minimum detectable effect sizes are to these assumptions. For comparison, in the Finnish feasibility study the prevalence of serious adverse outcomes was 3.7% = (38384/1031778) among all women, and according to EUROCAT 2015, the prevalence of malformation outcome among all women in the EU is 2.6%. The anticipated sample sizes in study cohorts 1-6 are:

- Cohort 1: 294 (80% of 368) for MS pregnancies exposed only to IFN- $\beta$ .
- Cohort 2: 368 (22% of 1671) for MS pregnancies exposed to IFN- $\beta$  regardless of exposure to other MSDMDs.
- Cohort 3: 1270 (76% of 1671) for MS pregnancies unexposed to any MSDMD.
- Cohort 4: 1303 (78% of 1671) for MS pregnancies unexposed to IFN- $\beta$ .
- Cohort 5: 33 (Cohort 4 size – Cohort 3 size = 1303 – 1270 = 33) for MS pregnancies exposed to MSDMDs except IFN- $\beta$  or glatiramer acetate (Copaxone®) or dimethyl fumarate (Tecfidera®).
- Cohort 6: Approximately 2.9 Million pregnancies for women from the general population in FIN, SWE and NOR without MS diagnosis based on the based on the feasibility study (cf. Annex 1).

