With these sample sizes and baseline outcome prevalence, the minimum detectable effect size between the MS women exposed to IFN- $\beta$  only (cohort 1) vs. MS women unexposed to any MSDMDs (cohort 3) is 1.72 in terms of RR using 80% power and a 5% two-sided significance level. If the background prevalence calculated among MS pregnancies unexposed to any MSDMD's would be closer to that in the whole population, e.g. 6%, 5%, 4% or 3%, the respective minimum detectable effect sizes would be 1.81, 1.91, 2.04, and 2.23. Regarding the comparison of a composite serious adverse pregnancy outcome between women with MS exposed to IFN- $\beta$  only (cohort 1) vs. unexposed to IFN- $\beta$  regardless of exposure to other MSDMDs (cohort 4), the minimum detectable effect size (RR) is approximately 1.77. Regarding the comparison of the composite serious adverse pregnancy outcome between women with MS exposed to IFN- $\beta$ s regardless of exposure to other MSDMDs (cohort 2) vs. unexposed to any MSDMD (cohort 3), the minimum detectable effect size (RR) is approximately 1.66.

The sample size calculations were performed using the `bpower` function of the R programming language (<http://www.r-project.org>).

**Table 5: The estimated numbers of all MS pregnancies and MS pregnancies unexposed to IFN- $\beta$ s available for the study during the study period by country.**

Country and study period		ALL MS Pregnancies	MS Pregnancies unexposed to IFN- $\beta$ s 
Country	Study period	Number of pregnancies	Number of pregnancies
Finland	1 Jan 1996 – 31 Dec 2014	777 	606 
Sweden	1 Jul 2005 – 31 Dec 2014	482 	376 
Norway	1 Jan 2004 – 31 Dec 2014	412 	321 
TOTAL		1671	1303

1) Estimated as 433 from time period 1 Jan 1996 – 31 Dec 2010 plus 4\*86 MS pregnancies from four additional years 2011 – 2014 where 86 denotes the number of MS pregnancies in 2010

2) Estimated as 329 MS births from Jul 2005 – 31 Dec 2011 plus (329 / 6.5) MS births from three additional years 2012 – 2014.

3) Estimated as 330 MS births from 1 Jan 2004 – 31 Dec 2014 divided by (1-0.2) where 0.2 denotes the estimated abortion prevalence

4) Estimated as the number of ALL MS PREGNANCIES x 78% where 78% denotes the estimated proportion of MS pregnancies unexposed to IFN- $\beta$  regardless of exposure to other MSDMDs

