### **Relevance of results to the European IFN- $\beta$ Pregnancy Registry**

Results of this retrospective cohort study are not directly comparable with the information derived from the European IFN- $\beta$  Pregnancy Registry. Available information on disease severity and other confounding factors differs between the health registers and the European IFN- $\beta$  Pregnancy Registry and in some cases is missing, such that the rates cannot be adjusted to be comparable. In addition, the pregnancy cases included in the Nordic health registers are population-wide and are not based on a sample, whereas the European IFN- $\beta$  Pregnancy Registry is based on spontaneous reports.

Furthermore, study and exposure periods differ between the countries in this study and follow-up periods in the European IFN- $\beta$  Pregnancy Registry. Also, it is known that there are regional and international differences in MSDMD treatment practices, MSDMDs on market and prevalence of MS. With the available data in this study we aim to partially control for some of these variations by stratification and adjustment for country, hospital district, year of pregnancy outcome, maternal age at LMP, time since MS diagnosis and duration of IFN- $\beta$  treatment.

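### Duration of MS treatment is a candidate confounder although in cohort 1 it includes the IFN-beta exposure itself; if harm rises with duration, the adjusted RR is pulled towards 1

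*Protocol*

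**What the plan says.** Section 9.7.3 plans two log-binomial models for the primary comparisons. The base model has a fixed covariate list without treatment duration. The adjusted model is built by variable selection from the base covariates plus further candidates, which include "number of foetuses in pregnancy (single vs. multiple), time since MS diagnosis and duration of MS treatment as available in the data sources". Section 9.4 lists the same item among the potential confounders and effect modifiers: "time since MS diagnosis, duration of MS treatment, number of previous abortions, smoking status during pregnancy". The Abstract (section 4, data analysis) also treats it as a potential confounder. Section 9.9, on relevance to the European registry, includes among the variables for stratification and adjustment "time since MS diagnosis and duration of IFN"-beta treatment.

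Selection has three relevant steps: a univariate screen against the outcome at P 0.25; a trial addition of the covariates that failed the screen, retained at likelihood-ratio P<0.1; and iterative reduction at likelihood-ratio P<0.1.

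Sections 8 and 9.4 define cohort 1 as pregnancies with an IFN-beta purchase in the six months before LMP or during pregnancy and no other MSDMD in the exposure window. Cohort 3 has no MSDMD purchase in that window, so it can include women treated earlier. The protocol does not say how duration is measured or what value a never-treated woman receives.

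**The concern.** The research question in section 8 is whether IFN-beta exposure before or during pregnancy has an adverse effect, which is a total effect of exposure. In cohort 1, duration of MS treatment is largely duration of IFN-beta, so the covariate is one dimension of the exposure and not only background disease. With duration beside the exposure indicator, the exposure RR compares exposed and unexposed pregnancies at equal duration. Any harm that builds up with years of use is credited to the duration coefficient and leaves the reported exposure RR.

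The selection rule adds an asymmetry. A covariate survives by being associated with the outcome, so duration is retained most often when risk depends on duration. In a safety study, an adjusted RR moved towards 1 in that situation could be read as reassurance.

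**Working it through.** **Inputs from the protocol (section 9.5).** "Cohort 1: 294 (80% of 368) for MS pregnancies exposed only to IFN"-beta; "Cohort 3: 1270 (76% of 1671) for MS pregnancies unexposed to any MSDMD"; baseline prevalence "7.3% (= 24/331, based on the feasibility study in Finland, cf. Annex 1"); a detectable RR that "is 1.72 in terms of RR using 80% power and a 5% two-sided significance level".

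**Reproducing the plan's figure.** The test is for two proportions with the variance pooled under the null.
- p0 = 24/331 = 0.0725; p1 = 1.72 × 0.0725 = 0.1247; difference = 0.0522.
- Pooled p = (294 × 0.1247 + 1270 × 0.0725)/1564 = 0.0823.
- Null SE = √[0.0823 × 0.9177 × (1/294 + 1/1270)] = 0.01779.
- Alternative SE = √[0.1247 × 0.8753/294 + 0.0725 × 0.9275/1270] = 0.02060.
- z = (0.0522 − 1.96 × 0.01779)/0.02060 = 0.84, so power is 0.80. The stated 1.72 reproduces.

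**Assumptions, because the protocol gives none.** Cohort 1 duration is gamma with shape 2 and scale 1.5 (mean 3 years). Former users make up 10, 30 or 60% of cohort 3, with gamma durations of shape 2 and scale 1 (mean 2 years); the rest have duration zero. Past treatment carries no risk. Harm is either RR = 1 + 0.24 × years in cohort 1 (average 1 + 0.24 × 3 = 1.72) or a constant RR of 1.72.

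**Model.** Log-link Poisson regression with robust SE, comparing cohort 1 with cohort 3, with duration the only candidate and exposure always kept. Duration is retained if its likelihood-ratio P<0.1. This simplifies the stated procedure, but whether or not duration passes the first screen, it must meet P<0.1 to stay.

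**Results when harm rises with duration:**

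| Former users in cohort 3 | Passes 0.25 screen | Kept at P<0.1 | Median reported RR | Power |
|---|---|---|---|---|
| 10% | 96% | 48% | 1.41 | 44% |
| 30% | 93% | 40% | 1.53 | 54% |
| 60% | 85% | 35% | 1.63 | 71% |

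Without duration the RR is about 1.72 and power about 80% throughout. Separate runs of this set-up differ by a few points, at most about 7 in power.

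**Results when harm is constant.** Duration is kept in about 10-12% of runs, the RR is unbiased on average, and power is about 75-78%.

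**Sensitivity to the assumptions.** A second set of runs gave former users the same 3-year mean and set cohort 1 durations between 0.1 and 10 years. With harm proportional to duration:
- 0% former users: kept 54%, median RR 1.29, power 37%.
- 30% former users: kept 28%, median RR 1.63, power 71%.
- 60% former users: kept 23%, median RR 1.68, power 77%.

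If only half of the harm depends on duration and cohort 3 has no former users, duration is kept in 24% of runs, the median RR is 1.61 and power is 61%.

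**The case against.** Several points on the other side carry weight.

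- **Conditional effect.** A reader might infer that the adjusted model always removes part of the IFN-beta effect. It does so only if harm grows with duration of use, and nothing in the protocol establishes such a gradient.
- **Pruning.** A reader might take the 0.25 screen as the entry rule and conclude that power falls to 21, 39 or 63% with RRs of 1.30, 1.43 or 1.55. Those figures arise only when duration is forced into every model. Section 9.7.3 prunes at P<0.1, and the loss after pruning is smaller.
- **Overlap.** A reader might say that the adjusted contrast has no data behind it. That holds only against never-treated women. Former users in cohort 3 supply overlap, and section 9.3.1.1 says the Finnish reimbursement certificate is issued when MSDMD treatment starts, which makes past treatment likely in part of Finnish cohort 3. Their share is unknown.
- **Truncation.** A reader might infer that duration is cut off where the Swedish and Norwegian prescription registers begin. Section 9.3.1.1 says both countries' MS registers also hold treatment data, so the documents do not support this.
- **Safeguards.** The base model omits duration and is reported, and step 4 requires the effect of adding and removing variables to be shown. These make a shift visible. They do not correct the adjusted RR. The base model also has a separate weakness: its teratogenic-medication covariate draws on the Annex 3 category D list, which contains the IFN-beta codes L03AB07 and L03AB08.
- **Severity proxy.** Section 9.9 says disease severity is not available from all sources, so treatment history is a defensible proxy. This stands, but it supports a history variable that ends before the exposure window, not total duration.

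**Conclusion.** The point holds as a conditional one. The protocol names as a candidate confounder a variable that, in cohort 1, includes the exposure being assessed. That is a stated choice, not a detail left to the SAP. If harm rises with duration, the adjusted RR is pulled towards 1. Under the main assumptions a true average RR of 1.72 is reported at a median of about 1.4 to 1.6, with power of about 44 to 71% in place of 80%. Across the alternative duration assumptions with harm proportional to duration, the result runs from 1.29 and 37% to 1.68 and 77%. If harm is constant, the cost is a small loss of power and no average bias.

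The direction does not depend on the assumed durations; the size does. Only cohort 1 against cohort 3 was simulated. The same definitional overlap applies to cohort 1 against cohort 4 and to the secondary cohort 2 against cohort 3 comparison, without a size attached.

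**What to change.** Remove duration of MS treatment, and duration of IFN-beta treatment, from the adjustment covariates of the cohort comparisons in the Abstract and sections 9.4, 9.7.3 and 9.9. Keep time since MS diagnosis as a candidate. If treatment history is wanted as a severity proxy, define it identically in both cohorts on MSDMD use before the exposure window only: earlier than six months before LMP, or nine months for mitoxantrone and cladribine, matching section 9.4. Use total duration only descriptively, as objective 5 already does, or as a dose-response analysis within cohort 1.

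The change is to wording and needs no new data. The price is slightly less control for severity as reflected in treatment history.

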Of these pregnancies, 76% (n=1270) are estimated to be unexposed to any MSDMDs, 22% (n=368) exposed to IFN- $\beta$  regardless of exposure to other MSDMDs, and 18% (n=294) exposed to IFN- $\beta$  only. With an anticipated background rate of 7.3% for the serious adverse pregnancy outcome, the minimum detectable effect size between the study cohorts of MS women exposed to IFN- $\beta$  only vs. MS women unexposed to any MSDMDs is 1.72 in terms of relative risk (RR) with an 80% power and 5% significance level.

**Data analysis:** The individual patient-level data from each country will be pooled into a single dataset and analyses will be conducted using the pooled dataset. The study cohorts will be characterised by country of residence, university hospital district, maternal age at LMP, year of pregnancy outcome, pre-pregnancy weight, pre-pregnancy body mass index (BMI), number of previous pregnancies, number of previous abortions, smoking status during pregnancy, number of foetuses in pregnancy (single vs. multiple), any chronic diseases, exposure to any teratogenic medications including steroids, time since MS diagnosis, and duration of MS treatment. These variables are also used as potential confounders when comparing the pregnancy outcomes between the study cohorts.

The descriptive statistics including number of events (n) and prevalence (%) will be presented for each pregnancy outcome in each study cohort separately. Descriptive analyses of the pregnancy outcomes within each study cohort will be further stratified by country, year of pregnancy outcome, maternal age at LMP, any chronic diseases, exposure to any teratogenic medication including steroids, time since MS diagnosis, duration of MS treatment, gestational age, and weight of the newborn as relevant for specific pregnancy outcomes.

The prevalence of the pregnancy outcomes will be further compared between the study cohorts using log-binomial regression with adjustments for i) baseline potential confounders (country, year, maternal age at LMP, previous pregnancies, chronic diseases, exposure to teratogenic medications including steroids) and ii) all relevant confounders. The RR estimates with 95% confidence intervals (CI) and associated p-values will be reported for these comparisons and for confounders used in the model. Confounding factors will be taken into account in the analyses according to availability and available time period from each register source.

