**Table 1: Definition of the study cohorts according to exposure to IFN- $\beta$  and other MSDMDs.**

Exposure status by IFN- $\beta$ and other MSDMD	Women with MS			Women without MS
	Unexposed to other MSDMD	Exposed to other MSDMD	Total	
Exposed to IFN-<math>\beta</math>	Cohort 1 Exposure to IFN- $\beta$ only	Exposed to both IFN- $\beta$ and other MSDMD (group not studied)	Cohort 2 All patients with IFN- $\beta$ exposure regardless of exposure to other MSDMDs	NA
Unexposed to IFN-<math>\beta</math>	Cohort 3 No exposure to any MSDMDs	Cohort 5 Only other MSDMD excluding IFN- $\beta$ or glatiramer acetate (Copaxone®) or dimethyl fumarate (Tecfidera®)  (for sensitivity analysis only)	Cohort 4 All patients with no IFN- $\beta$ exposure regardless of exposure to other MSDMDs	Cohort 6 Women from the general population without MS diagnosis

**The primary objectives** are:

1. To estimate the prevalence of the following pregnancy outcomes in the above four study cohorts 1 – 4:
  - Serious adverse pregnancy outcome defined as a composite endpoint including elective TOPFA, MCA or stillbirth
  - Elective TOPFA or elective termination for other reasons (assessment not possible in SWE as no register available)
  - Stillbirth
  - Live birth
  - MCA
2. To compare the prevalence of each of the outcomes in objective 1 between:
  - i) women with MS exposed to IFN- $\beta$  only (cohort 1) vs. unexposed to any MSDMDs (cohort 3) and
  - ii) women with MS exposed to IFN- $\beta$  only (cohort 1) vs. unexposed to IFN- $\beta$  regardless of exposure to other MSDMDs (cohort 4).

**The secondary objectives** are:

3. To compare the prevalence of the following pregnancy outcomes between:
  - i) women with MS exposed to IFN- $\beta$  regardless of exposure to other MSDMDs (cohort 2) vs. unexposed to any MSDMDs (cohort 3):
    - Serious adverse pregnancy outcome
    - Elective TOPFA or elective termination for other reasons (not possible in SWE)
    - Stillbirth
    - Live birth
    - MCA
4. To estimate the prevalence of a) ectopic pregnancies and b) spontaneous abortions in the study cohorts 1, 2, 3 and 4 and to compare these prevalences separately between:
  - i) women with MS exposed to IFN- $\beta$  only (cohort 1) vs. unexposed to any MSDMDs (cohort 3),
  - ii) women with MS exposed to IFN- $\beta$  only (cohort 1) vs. unexposed to IFN- $\beta$  regardless of exposure to other MSDMDs (cohort 4), and

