### 9.7.4 Analysis of secondary objectives

With regard to objective #3, similarly as in the analysis of the primary objectives, the prevalence of the pregnancy outcomes (i.e. serious adverse pregnancy outcome, elective TOPFA, stillbirth, live birth and MCA) will be compared between the study cohorts specified in Section 8.

With regard to objective #4, the descriptive statistics including number (n) and prevalence (%) of ectopic pregnancies and spontaneous abortions will be presented in each study cohort separately. The prevalence of these pregnancy outcomes will be compared between the study cohorts specified in Section 8.

With regard to objective #5, the descriptive statistics (n and %) of the pregnancy outcomes (i.e. serious adverse pregnancy outcome, elective TOPFA, stillbirth, live birth and MCA) will be further described for study cohorts 1 – 4 stratified by country, year of pregnancy outcome, maternal age at LMP, any chronic diseases, exposure to any teratogenic medications including steroids, time since MS diagnosis, duration of MS treatment, gestational age and weight of the newborn as relevant for specific pregnancy outcomes and as the number of events allow.

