### 9.7.6 Sensitivity analyses

- Lack of information on terminations of pregnancy due to foetal anomalies from SWE may yield underestimation of the prevalence of MCA in the study population. In FIN, 10.5% of total cases with MCAs were diagnosed and recorded in TOPFAs between 1993 and 2010. However, this may bias the study results on MCAs if the risk for TOPFA differs between women with different MSDMD exposures or MS exposure in SWE. Separate analyses will be performed on MCAs for the Norwegian and the Finnish data including pregnancy terminations, stillbirths and live births, and another analysis including live births only. The analyses will also be stratified by country as the follow-up times of the newborn babies for recording the malformations in MBRs or Malformation Register may vary between the countries.

- Information on pregnancy terminations is available from GW 12 onwards from the Norwegian data, and therefore, information on early pregnancy terminations conducted before GW 12 could result in incomplete data. Therefore separate analyses by trimesters on pregnancy terminations will be performed.
- In additional sensitivity analyses on MCAs, outcomes will be assessed where exposure occurred prior to pregnancy and through to the end of the first trimester of pregnancy. Also, an analysis of MCA outcomes from live births only will be performed.
- As there is a geographical variation in MS prevalence not only between countries but also within countries, descriptive statistics will be conducted by country and university hospital district level. Country and region will also be included in the multivariate analyses.
- Possible changes in diagnostic criteria and developments in examination and treatment throughout time, as well as trends in obstetric care may influence the estimated prevalence. The study periods also vary between the countries, which may reflect the deviation in the results. Therefore the year of pregnancy outcome will be taken into account in the descriptive statistics and analyses. By taking into account the data from 1 Jan 2005 to 31 Dec 2014 from each country (time period in which the data is available i.e. overlaps for all 3 countries), a separate sensitivity analysis of the primary objective will be provided as well.

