### 9.7.7 Missing data

For study variables, if a variable is totally missing from a database, it will be excluded from the analysis. If a variable is missing for only some of the patients a missing data category will be added and used in the analysis. In addition, to investigate the robustness of the variable selection procedure (section 9.7.3) to missing data, if a candidate covariate is missing from over one quarter of patients, missing values will be imputed multiple times and the variable selection re-performed using each of the complete (imputed) data sets (Wood et al. 2008). Results for models including predictors that appear in i) any, ii) at least half, and iii) all models selected using the imputed data sets will be reported as part of the sensitivity analyses (Wood et al. 2008 section 2.4.3).

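### For TOPFA alone and for stillbirth, the fixed base log-binomial model may have no exposed events, and the 1:10 event limit does not reach it

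*Protocol*

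**What the plan says.** - **Scope.** Primary objective 2 (Section 8) is "To compare the prevalence of each of the outcomes in objective 1 between" cohorts 1 and 3, and cohorts 1 and 4. The outcomes in objective 1 are the composite, elective terminations, stillbirth, live birth and major congenital anomaly (MCA).
- **Method.** The Abstract states: "The prevalence of the pregnancy outcomes will be further compared between the study cohorts using log-binomial regression". It gives two levels of adjustment and reports RR, 95% CI and p-value. Section 9.7.4 treats objective 3 "similarly as in the analysis of the primary objectives, the prevalence of the pregnancy outcomes" and names elective TOPFA and stillbirth. The modelling paragraph of 9.7.3 names only the composite, but no other comparison method is given for the single outcomes.
- **Base model (9.7.3).** It is adjusted for "country, year of pregnancy outcome, maternal age at LMP, number of previous pregnancies, any chronic diseases, and exposure to any teratogenic medications including steroids", with no condition on the number of events.
- **Missing values (9.7.7).** "If a variable is missing for only some of the patients a missing data category will be added and used in the analysis", which adds further parameters.
- **Event limit (9.7.3, step 4).** When outcomes are few, "the final adjusted model will be limited to a covariate-outcome ratio of 1 covariate: 10 outcomes to avoid over-adjustment". The unit is the covariate, not the parameter.
- **Other caveats.** Section 9.7.4 makes allowance for the number of events only in the stratified descriptive work of objective 5. Section 9.9 (Study power) concedes that single outcomes are not powered. It does not restrict or replace the regression for them.

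**The concern.** The protocol adopts a stability rule and then exempts the larger of its two models when events are few. With 5 to 9 events, step 4 allows no covariates in the adjusted model, while the base model for the same outcome still carries six plus exposure. The adjusted model would then be smaller than the base model.

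The practical stake is separate. If cohort 1 has no event, the log-binomial estimate of the log RR runs to minus infinity, and a Wald interval or p-value taken from the fit means nothing. This could happen for comparisons listed under a primary objective of a safety study requested by a regulator. Low power, which Section 9.9 concedes, means a wide interval. Here the specified estimate may not exist at all.

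**Working it through.** **The plan's own figure.** Inputs from Section 9.5: cohort 1 = 294, cohort 3 = 1270, background 7.3% (24/331), 80% power, two-sided 5%. A two-proportion calculation with pooled null variance gives a minimum detectable RR of 1.717 at 7.3% and 1.720 at 24/331. The stated 1.72 is reproduced, so these cohort sizes are used below.

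**Slopes in the base model.** Exposure 1, country 2 (three countries), and one each for year, age, previous pregnancies, chronic disease and teratogenic medication: 1 + 2 + 5 = 8. For TOPFA, Sweden has no termination data, so country takes 1 and the total is 7. Both are minima, before missing-data categories or categorical coding.

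**TOPFA alone.**
- Share of MCAs, from 9.7.6: "In FIN, 10.5% of total cases with MCAs were diagnosed and recorded in TOPFAs between 1993 and 2010".
- MCA prevalence: 2.6% (the EU figure in 9.5), up to 7.3%, the whole composite and therefore an upper bound.
- Finland + Norway: 777 + 412 = 1189 pregnancies. Cohort 1 is 1189 × 294/1671 = 209; cohort 3 is 1189 × 0.76 = 904.

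| MCA prevalence | TOPFA rate (× 0.105) | Events, cohort 1 | Events, cohort 3 | Chance of 0 in cohort 1, (1 − p)^209 |
|---|---|---|---|---|
| 2.6% | 0.273% | 0.6 | 2.5 | 56% |
| 7.3% | 0.767% | 1.6 | 6.9 | 20% |

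**Stillbirth.** No rate is stated, so a range is assumed. Subtracting 2.6% from the all-women composite of 3.7% (9.5) gives 1.1%. That is only rough, because the two figures come from different populations and the composite also holds TOPFA.

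| Assumed rate | Events, cohort 1 (× 294) | Events, cohorts 1 + 3 (× 1564) | Chance of 0 in cohort 1, (1 − p)^294 |
|---|---|---|---|
| 0.3% | 0.9 | 4.7 | 41% |
| 0.5% | 1.5 | 7.8 | 23% |
| 1.0% | 2.9 | 15.6 | 5% |
| 1.1% | 3.2 | 17.2 | 4% |

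**Does the number of slopes matter?**
- The chance of a zero cell depends only on the rate and the size of cohort 1. A crude 2 × 2 table has the same zero.
- In simulations under RR = 1, the median ratio of upper to lower 95% limit for exposure, where estimable, was about 64, 30 and 13 for the base model at 0.4%, 0.5% and 1.0%. The crude analysis gave 63, 30 and 13. Coverage was 93% to 98%.
- What the extra slopes add is covariate terms without finite estimates. In 200 data sets per scenario, at least one coefficient of any kind had no finite estimate in 75%, about 50% and 17% at stillbirth rates of 0.35%, 0.5% and 1.1%. For TOPFA it was 88% to 46% over 0.27% to 0.77%. For the composite at 7.3% or 3% it was 0%. These shares rest on assumed covariate distributions (chronic disease 15%, teratogenic drugs 30%).

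**What an exact interval gives.** Take 0/294 against 5/1270. Given five events, each falls outside cohort 1 with probability 1270/(1270 + 294 × RR). Setting the fifth power of this to 0.025 gives RR = (1 − 0.025^(1/5))/0.025^(1/5) × 1270/294 = 4.7. The result is RR 0, exact 95% CI 0 to 4.7.

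**The limit applied to the composite.** 1564 × 7.3% = 114 events would allow 11 parameters, so all 8 slopes fit. At the protocol's own lower scenarios of 5% and 3%, 78 and 47 events would allow 7 and 4.

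**The case against.** **The number of slopes is not the cause.** A reader might infer that the RRs fail because eight slopes are fitted, or that the base model inflates the interval. The figures do not support that. Zero cells arise just as often without covariates, and the base-model and crude intervals are nearly the same width. Extending the 1:10 limit would remove the inconsistency and the non-finite covariate terms, but not the zero cells. This part of the objection stands.

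**Stillbirth rests on an assumption.** A reader might also infer that about one stillbirth in cohort 1 follows from the protocol's numbers. It does not. At the rough 1.1% there are about 3 events, and none is seen only 4% of the time. This stands too.

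**TOPFA may not be analysed alone.** Section 8 and Table 6 word the outcome as TOPFA or termination for other reasons. If the two are combined, the 0.2 abortion prevalence in the notes to Table 5 gives about 0.2 × 209 = 42 events in cohort 1, and the problem does not arise. Section 9.5 leaves open which losses the 0.2 covers, but even a quarter of it gives about 10. Sections 9.7.3 and 9.7.4 nevertheless name elective TOPFA alone.

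**The interval type is not stated.** The protocol promises 95% CIs and mentions Wald only for covariate screening. A profile-likelihood upper limit for 0/294 against 5/1270 is finite, about 2.0 (crude). But at RR = 2.0 the chance that all five events miss cohort 1 is (1270/1858)^5 = 15%, far above 2.5%. That limit is too optimistic to settle the matter.

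**Such details belong in the SAP.** Non-convergence fallbacks and coding usually do, and their absence here is no fault. What the protocol itself fixes is an unconditional base model and a limit confined to the other model. Counts by cohort will be reported in any case, so a zero would be visible.

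**Conclusion.** The point holds in a limited form. The Abstract and Sections 8, 9.7.3 and 9.7.4, read together, commit TOPFA and stillbirth to a fixed base model that the protocol's only event limit does not reach.

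For TOPFA alone, the chance of no exposed event, and so no finite exposure estimate, is 56% to 20%. This assumes that TOPFA is 10.5% of MCAs, that MCA prevalence is 2.6% to 7.3%, and that the planned exposure shares apply in Finland and Norway. For stillbirth it is 41% to 23% at an assumed 0.3% to 0.5%, and 5% to 4% at 1.0% to 1.1%.

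The documents do not support reading this as a threat to the primary composite at 7.3%. At 3% the limit would allow fewer covariates than the base model carries, which is inconsistent, but no simulated fit failed. The correction is worth making because it changes what can be reported for the rare components. It does not alter the main comparison.

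**What to change.** In 9.7.3 and 9.7.4:

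1. Keep the log-binomial base and adjusted models for the composite.
2. Apply the event limit to the base model as well, and count parameters (degrees of freedom) rather than covariates, so that the adjusted model cannot end up smaller than the base model. State in advance the order in which base covariates are dropped, since a composite prevalence of 5% or 3% would trigger the limit.
3. For outcomes with too few events, for example fewer than about 10 in total or none in one cohort, replace the base-model RR and p-value. Report counts with a crude or country-stratified RR and an exact or mid-P interval, or a Firth-type penalised estimate. The threshold is a judgement and should be fixed before the data are seen.
4. State whether TOPFA is compared alone or together with other terminations.

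The cost is a few sentences and standard R functions. The real downside is less covariate adjustment for the rare components.
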